6.3 Dose modifications

6.3.1 Dose modification and dose delay

For patients who do not tolerate the protocol-specified dosing schedule, dose interruptions and/or reductions are either recommended or mandated in order to allow patients to continue the study treatment.

These dose modifications are summarized in [Table 6-2](#). Deviations to mandatory dose interruptions and/or reductions are not allowed. Permanent treatment discontinuation is mandatory for specific events indicated as such in [Table 6-2](#).

These dose changes must be recorded on the appropriate CRF.

Study drug (midostaurin/placebo)

[Table 6-2](#) describes toxicities (i.e., adverse drug reactions), laboratory values, or other assessments that require interruption or dose modification of study drug. Whether an AE that is not considered to be caused by the study treatment requires modifications needs to be assessed by the investigator. The need for modification in case of non-drug related AEs depends on the type of these AEs.

During induction and consolidation therapies, modifications must be done in case of non-hematologic toxicities, i.e., ADRs (pulmonary, cardiac or other non-hematologic toxicities).

During post-consolidation therapy, modifications must be done in case of hematologic and non-hematologic toxicities (pulmonary, cardiac or other non-hematologic toxicities).

If interruptions occur, missed doses of study drug will not be made up.

Study drug interruptions of greater than 28 consecutive days will require discontinuation from study treatment, unless the patient undergoes HSCT as in that case the drug interruption can be longer than 28 consecutive days (please refer to section 6.1.1 for more detailed information).

Cytarabine

Doses will be modified only during the consolidation phase with intermediate-dose cytarabine and in case of neurotoxicity, hematology and non-hematology toxicity. Please refer to [Table 6-2](#).

Idarubicin/ Daunorubicin

Doses will be modified during induction phase in case of hepatotoxicity, hematology and non-hematology toxicity. Please refer to [Table 6-2](#).

[figure not shown]
[figure not shown]
[figure not shown]

Table 6-2 Criteria for dose reduction/interruption and re-initiation of midostaurin/placebo, daunorubicin/idarubicin and cytarabine treatment for adverse drug reactions

[figure not shown]
Dose modifications for midostaurin/placebo	
Hematologic toxicities	

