During induction and consolidation cycles	No dose modifications are required for hematologic toxicity due to midostaurin/placebo during induction and consolidation therapy.
During post-consolidation cycles	In the presence of grade 4 neutropenia during post-consolidation therapy, midostaurin/placebo must be held until Absolute Neutrophil Count (ANC) $\geq 1.0 \times 10^9/L$. Once ANC $\geq 1.0 \times 10^9/L$, then resume midostaurin/placebo at the previous dose. If neutropenia persists for more than two weeks, then discontinue midostaurin/placebo protocol therapy.
Non-Hematologic toxicities:	

 Pulmonary toxicities 	
During induction, consolidation and post-consolidation cycles	For \geq grade 3 pulmonary infiltrate , midostaurin/placebo must be interrupted for the remainder of the cycle. Resume midostaurin/placebo at the same dose when infiltrate resolves to \leq grade 1. Missed doses of midostaurin/placebo will not be made up. If there is no improvement after 28 days, the patient must be discontinued from study drug.

 Cardiac Toxicity 	
During induction, consolidation and post-consolidation cycles	
 For QTcF interval > 470 ms and ≤ 500 ms, check magnesium and potassium levels and correct any abnormalities. If possible, stop any medications that may prolong the QTcF interval. Decrease midostaurin/placebo to 50 mg once daily for the remainder of the cycle. Resume midostaurin/placebo at the initial dose in the next cycle provided that QTcF interval improves to ≤ 470 ms at the start of that cycle. Otherwise continue midostaurin/placebo 50 mg once daily. For QTcF interval > 500 ms and/or QTcF prolongation >60 ms from baseline, check magnesium and potassium levels and correct any abnormalities. Hold or interrupt midostaurin/placebo for the remainder of the cycle, and, if possible, stop any medications that may prolong the QTcF interval. If QTcF improves to ≤ 470 ms just prior to the next cycle, resume midostaurin/placebo at the initial dose. If QTcF interval is not improved to ≤ 470 ms in time to start the next cycle, midostaurin/placebo may be held up to 28 days. If there is no improvement after 28 days, the patient must be discontinued from study drug.

 Other Non-Hematologic toxicity 	

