6.3.2 Dose adjustments for QTcF prolongation

In case of QTcF >500 ms, (or QTcF prolongation >60 ms from baseline)

1. Assess the quality of the ECG recording and the QT value and repeat if needed
2. Interrupt study treatment
3. Determine the serum electrolyte levels (in particular hypokalemia, hypomagnesemia). If abnormal, correct abnormalities before resuming study drug treatment.
4. Review concomitant medication associated with QT prolongation, including drugs with a “Known”, “Possible”, or “Conditional risk of Torsades de Pointes”, and drugs with the potential to increase the risk of study drug exposure related QT prolongation
5. Check study drug dosing schedule and treatment compliance
6. Consider collecting a time-matched PK sample, and record time and date of last study drug intake.
7. Note that measurements of QTcF ≥ 480 ms shall be centrally verified on a copy of the original high quality recording that includes time and voltage scales

After confirming ECG reading at site, if QTcF > 500 ms

- Interrupt study treatment
- Repeat ECG and confirm ECG diagnosis by a cardiologist
- If QTcF confirmed > 500 ms:
 - Correct electrolytes, eliminate culprit concomitant treatments, and identify and address clinical conditions that could potentially prolong the QT
 - Consult with a cardiologist (or qualified specialist)
 - Increase cardiac monitoring as indicated, until the QTcF returns to ≤ 470 ms.
- After resolution to ≤ 470 ms, consider re-introducing treatment at reduced dose, and increase ECG monitoring for the next treatment(s):
 - If QTcF remains ≤ 500 ms after dose reduction, continue planned ECG monitoring during subsequent treatment
 - If QTcF recurs > 500 ms after dose reduction, discontinue patient from study drug.

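### After confirmed QTcF >500 ms the protocol gives two restart doses without ranking them, and its only mandatory recurrence stop does not reach a patient restarted at full dose

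*Protocol*

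**What the plan says.** Two parts of Protocol Section 6.3 deal with severe QTcF prolongation.

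**Table 6-2, cardiac toxicity row (Section 6.3.1).** The trigger is QTcF >500 ms and/or an increase of >60 ms from baseline. The first step is "Hold or interrupt midostaurin/placebo for the remainder of the cycle". If QTcF then improves to ≤470 "ms just prior to the next cycle, resume midostaurin/placebo at the initial dose". If it does not, the drug may be held for up to 28 days, and the patient must come off study drug if there is still no improvement. A lower band, >470 to 500 ms, has its own rule: "Decrease midostaurin/placebo to 50 mg once daily for the remainder of the cycle". That is the only reduced midostaurin level the protocol names.

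**Section 6.3.2.** The general steps cover QTcF >500 ms or >60 ms from baseline. The restart steps come under a narrower lead-in: "After confirming ECG reading at site, if QTcF > 500 ms". Once QTcF is back to ≤470 ms, the instruction is to "consider re-introducing treatment at reduced dose, and increase ECG monitoring for the next treatment(s". No dose level is given. If QTcF exceeds 500 ms again "after dose reduction, discontinue patient from study drug".

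**The text around the table.** Section 6.3.1 states that "Deviations to mandatory dose interruptions and/or reductions are not allowed" and that "Permanent treatment discontinuation is mandatory for specific events indicated as such in" Table 6-2.

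**The concern.** One severe event has two restart instructions, and both are current text. One site can restart at the initial dose and another at a reduced dose of its own choosing, and each can point to the protocol.

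The restart dose also decides what a second event triggers. A patient who was reduced must stop if QTcF exceeds 500 ms again. A patient who resumed full dose, as Table 6-2 directs, is outside the wording of that stop. The mandatory consequence is therefore missing for the patient on the higher dose.

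What is at stake is patient safety and consistent handling across a planned 150 to 180 sites.

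**Working it through.** There is no design figure to reproduce, so the check is a comparison of the texts.

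**Step 1. The two rules side by side, for confirmed QTcF >500 ms.**

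| Element | Table 6-2 | Section 6.3.2 |
|---|---|---|
| Immediate action | Hold for the rest of the cycle | Interrupt; length not stated |
| Condition for restart | ≤470 ms before the next cycle | ≤470 ms |
| Restart dose | Initial dose | Reduced dose to be considered; level not named |
| Failure to improve | Stop after 28 days | Not addressed |
| Recurrence >500 ms | Not addressed | Stop, if the dose had been reduced |

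**Step 2. Is there a precedence rule?** Four places could supply one.

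- Section 6.3.1 forbids departures from mandatory interruptions and reductions. That supports keeping the rest-of-cycle hold, but it does not rank the two restart doses.
- Section 6.3.1 also ties mandatory discontinuation to events marked in Table 6-2. Recurrent QTcF >500 ms is not marked there.
- The Table 6-2 footnote bases modifications on the worst earlier toxicity. It gives no restart dose and no ranking.
- The ECG section (7.2.2.7.1) refers the reader to Section 6.3 as a whole, which contains both rules.

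None of the four settles the restart dose.

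**Step 3. What follows a recurrence above 500 ms?**

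- After a reduced-dose restart: mandatory discontinuation (Section 6.3.2).
- After a full-dose restart: the Table 6-2 hold applies again, as do the Section 6.3.2 steps (repeat ECG, cardiologist, reduced dose again to be considered). The mandatory QTcF stop that remains is for no improvement after 28 days. That addresses persistence, not recurrence.

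The same table does deal with recurrence elsewhere: a second neurotoxicity of grade 2 or higher leads to permanent discontinuation of intermediate-dose cytarabine. It has no counterpart for QTcF.

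**Step 4. Size of the dose difference.** The initial dose is 50 mg twice daily, 2 × 50 = 100 mg per day. If the unnamed reduced dose is 50 mg once daily, it is 50 mg per day, and 50/100 is one half. That level is borrowed from the >470 to 500 ms band, and Section 6.3.2 does not refer to it.

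**Step 5. The >60 ms trigger (secondary).** The restart steps in Section 6.3.2 are limited to QTcF >500 ms, so for a rise of >60 ms alone only Table 6-2 gives a restart criterion. That criterion is an absolute value, ≤470 ms. The trigger, baseline + 60, lies below 470 ms whenever baseline is below 470 − 60 = 410 ms. For a baseline of 405 ms the trigger is anything above 405 + 60 = 465 ms. A QTcF that falls from above 470 ms to 466 ms has improved to ≤470 ms, yet is still 466 − 405 = 61 ms above baseline. The restart criterion and the hold trigger are then both satisfied.

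**The case against.** The strongest reply is that the two sections can be read together. Section 6.3.2 says to consider a reduction, which gives discretion. Table 6-2 is then the default, and Section 6.3.2 lets the investigator go lower once electrolytes and culprit drugs have been dealt with. On that reading, patient-by-patient dosing is intended. This largely stands: a reader might infer two conflicting mandates, and the wording does not support that. But the protocol does not state the reconciling reading, and adopting it leaves the recurrence gap in place, because an investigator who follows the default never meets the condition for the mandatory stop.

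The second reply is that a recurrence is not left unmanaged. This also stands. Interruption, repeat ECG, cardiologist input and central verification at ≥480 ms all apply. So do the 28-day limits, discontinuation for unacceptable toxicity (6.1.5, 7.1.3), the investigator's right to stop (7.1.4) and DMC safety review about every 6 months (8.6). A reader might infer that the full-dose patient has no protection, which would be wrong. What is missing is a mandatory response to the recurrence itself beyond another hold and work-up.

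The third reply concerns remedy: stopping at any recurrence, whatever the dose, would skip the reduction that Section 6.3.2 offers, and Section 6.3.1 presents modifications as a way to keep patients on treatment. That is fair, and the fix below does not go so far.

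On the >60 ms trigger, it can be said that the table requires QTcF to have improved and holds the drug for the rest of the cycle first. So the text does not support inferring that a patient may restart as soon as the hold begins. The mismatch between an absolute restart criterion and a relative trigger remains.

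**Conclusion.** The point holds as a gap in safety wording. After confirmed QTcF >500 ms, the restart dose is left open between the initial dose and an unnamed lower one, and the only mandatory recurrence stop is conditional on a reduction that Table 6-2 does not require.

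Its size can be stated only in part. The restart doses differ by half the daily dose, on the assumption that the reduced dose is 50 mg once daily. The documents give no frequency for QTcF >500 ms, so the number of patients affected is unknown.

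Three further inferences should be resisted.

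- A fixed maximum number of full-dose restarts cannot be derived from the scheduled ECGs, because Table 7-7 also allows unscheduled ones whenever clinically indicated.
- A cumulative dose difference would rest on assumed doses and restart times, and its direction would change with the cycle of onset.
- Nothing here bears on EFS, OS or the error rates: both arms follow the same text under blinding.

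The SAP introduction records that the trial stopped for futility while some patients continued treatment. The practical value lies with patients still being dosed under this text and with any reuse of it.

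**What to change.** State one rule for QTcF >500 ms, worded identically in Table 6-2 and Section 6.3.2:

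1. Keep the hold for the remainder of the cycle.
2. Say which restart dose applies after recovery to ≤470 ms, and name the reduced level, for example 50 mg once daily.
3. If QTcF exceeds 500 ms again after a full-dose restart, require at least the named reduction, or discontinuation.
4. If it exceeds 500 ms again at the reduced dose, require discontinuation, as Section 6.3.2 already does.

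For the >60 ms trigger, add to the ≤470 ms criterion that QTcF must be no more than 60 ms above baseline before restart.

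The cost is wording in a protocol amendment or a clarification letter to sites. No new procedure, visit or ECG is needed. The choice of restart dose is clinical and belongs to the study's medical team; the need is that it be made once and stated in both places.

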6.1.1 Dosing regimen

[figure not shown]
On Day 1 of study treatment, the first dose of induction chemotherapy will be administered.

Daunorubicin/ idarubicin and cytarabine are approved drugs and will be sourced either according to local practice or centrally. Please refer to the Package Insert for complete guidelines for administration and for safety monitoring guidelines.

The dosage of daunorubicin/idarubicin and cytarabine will be adjusted based on body surface area (BSA) calculated before administration. To calculate BSA, the height at baseline and weight on the first day of the respective treatment cycle will be used.

Dose modification for obese patients:

There is no clearly documented adverse impact of treatment of obese patients when dosing is performed according to actual body weight. Therefore, all dosing is to be determined solely by the patient’s BSA as calculated from actual weight. This will eliminate the risk of calculation error and the possible introduction of variability in dose administration.

6.1.1.1 Treatment regimen:

First Induction:

- **Cytarabine** 200 mg/m²/day will be administered by continuous intravenous infusion (CIVI) on Days 1-7 (168 hour infusion).
- **Daunorubicin** 60 mg/m²/day *or* **idarubicin** 12 mg/m²/day will be administered intravenously by IV push (IVP) or short (30 minutes) infusion on Day 1-3.
- **Study drug (midostaurin** 50 mg [two 25 mg capsules] **or placebo** [2 capsules]) will be administered twice per day by mouth from Day 8 until 48 hrs prior to the start of next cycle (i.e. the morning of Day 27 if hematopoiesis recovers timely (cycle length of 28 days) or later if the cycle needs to be prolonged for blood count recovery). Patients should take their doses at approximately the same time each day, and approximately 12 hours should elapse between the morning and evening doses. On days that PK samples are obtained, the patient should take study drug during the clinic visit after the pre-dose PK sample and prior to post-dose PK samples, when instructed by the study staff. Each daily dose should be given with food and a glass of water (~240 mL). Patients should be instructed to swallow capsules whole and not chew capsules. If vomiting occurs, no re-dosing is allowed prior to the next scheduled dose. The soft capsules should be removed from the blister pack only shortly prior to administration. The capsules may have an unpleasant odor, which disappears a few seconds after the blister foil is opened.

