
During induction and consolidation cycles
 
During post-consolidation cycles
	
 • Grade 1/2: No dose modifications for any grade 1 or 2 non-hematologic toxicity. • Grade 3/4: If a patient experiences other grade 3/4 non-hematologic toxicity considered related to midostaurin/placebo, midostaurin/placebo will be interrupted until toxicity resolves to \leq grade 1. If the toxicity resolves prior to day 21, then restart at same dose to complete current cycle. Missed doses of midostaurin/placebo will not be made up. A study drug interruption in excess of 28 days will require discontinuation of study treatment. • Grade 1/2: Persistent grade 1 or 2 toxicity during post-consolidation therapy that patients deem to be unacceptable may prompt a study drug interruption for as long as 28 days. A study drug interruption in excess of 28 days will require discontinuation of study treatment. • Grade 3/4: For other grade 3/4 non-hematologic toxicities that are considered to be related to midostaurin/placebo, interrupt midostaurin/placebo. Resume midostaurin/placebo at the same dose when toxicity resolves to \leq grade 2. If midostaurin/placebo is held for more than 28 days, then discontinue midostaurin/placebo post-consolidation therapy.

Dose modifications for intermediate-dose cytarabine (IDAC) induction 2 if applicable and consolidation therapy
	

During Induction 2 if applicable and consolidation cycles
	
Dose reduction according to institutional guidelines except in case of neurotoxicity dose modifications as below: Contributions of concomitant medications to neurotoxicity should be assessed and other medications discontinued if possible.
 
For neurotoxicity \geq grade 2 due to intermediate-dose cytarabine, discontinue cytarabine for the remainder of the cycle. Intermediate-dose cytarabine may be considered at the next consolidation therapy cycle with a dose modification from 1500mg/m² to 1000mg in patients <60 years of age and from 1000mg/m² to 600mg/m² in patients \geq60 of age if the toxicity has resolved to \leq grade 1.
 
For a second occurrence of neurotoxicity \geq grade 2, intermediate-dose cytarabine should be permanently discontinued.

Dose modifications for daunorubicin		
	Dose reduction according to institutional guidelines except in case of hepatotoxicity dose modifications as below:	
During induction cycles	Total Bilirubin (mg/dL)	% daunorubicin dose to administer
	≤ 1.2	100%

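### Table 6-2 omits the per-m² unit from one reduced cytarabine dose, and Section 6.3.1 leaves out Induction 2, which the table covers

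*Protocol*

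**What the plan says.** **The dose.** Protocol Section 6.1.1 sets the basis for chemotherapy dosing: "The dosage of daunorubicin/idarubicin and cytarabine will be adjusted based on body surface area (BSA) calculated before administration". Under its note on obese patients it adds that "all dosing is to be determined solely by" BSA from actual weight. The neurotoxicity rule in Table 6-2 has these parts:

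- At grade 2 or higher, "discontinue cytarabine for the remainder of the cycle".
- Afterwards, "Intermediate-dose cytarabine may be considered at the next consolidation therapy cycle with a dose modification", provided the toxicity has resolved to grade 1 or less.
- For younger patients the change is from 1500 mg/m² "to 1000mg in patients <60 years of age". For patients aged 60 or over it is from 1000 mg/m² to 600 mg/m².
- A second episode means permanent discontinuation of intermediate-dose cytarabine.

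**The scope.** The cytarabine paragraph of Section 6.3.1 states: "Doses will be modified only during the consolidation phase with intermediate-dose cytarabine". It continues with the types of toxicity concerned and refers the reader to Table 6-2. The cytarabine row of that table is labelled "During Induction 2 if applicable and consolidation cycles", and the title of the block has the same scope. Section 6.3.1 also says: "Deviations to mandatory dose interruptions and/or reductions are not allowed".

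**The concern.** These are instructions a site acts on, so their unit and scope should be exact.

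The missing /m² turns a BSA-based dose into a flat one if read as printed. That would under-dose a patient under 60 who is re-challenged after neurotoxicity.

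The word restricting modification to consolidation excludes something the table includes. Patients without adequate remission after the first cycle receive intermediate-dose cytarabine in Induction 2 (Sections 4.2.1 and 6.1.1.1, Table 6-1), so the table's wider scope is real. A reader of the Section 6.3.1 sentence alone could doubt three things:

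- whether the stop for the rest of the cycle applies in Induction 2;
- whether reductions under institutional guidelines are allowed there;
- whether an Induction 2 episode counts as the first of the two that lead to permanent discontinuation.

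**Working it through.** **1. Is the missing unit isolated?** Count of intermediate-dose cytarabine doses stated in the protocol:

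| Place | Doses | With /m² |
|---|---|---|
| Section 6.1.1.1, Second Induction | 2 | 2 |
| Section 6.1.1.1, Consolidation | 2 | 2 |
| Table 6-1 (Induction 2 and Consolidation) | 4 | 4 |
| Table 6-2, neurotoxicity rule | 4 | 3 |
| Total | 12 | 11 |

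The other three doses in the Table 6-2 sentence kept their unit, so a fault in reading the PDF is unlikely. SAP Section 6.6 also collects the administered cytarabine dose in mg/m².

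**2. What does each reading imply?** With /m² restored, the cut for patients under 60 is 1 − 1000/1500 = 33%. This is close to the 1 − 600/1000 = 40% for patients aged 60 or over.

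For the literal reading, the dose per m² is 1000/BSA. The documents give no BSA, so 1.5 to 2.2 m² is assumed.

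| Assumed BSA (m²) | Flat 1000 mg as mg/m² | Below the intended 1000 mg/m² | Cut from 1500 mg/m² |
|---|---|---|---|
| 1.5 | 667 | 33% | 56% |
| 1.8 | 556 | 44% | 63% |
| 2.2 | 455 | 55% | 70% |

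The flat dose also breaks the age ordering of the regimen. It equals 600 mg/m² at BSA = 1000/600 = 1.67 m². Above that, a patient under 60 would receive less than a patient of the same size aged 60 or over. At 1.8 m² the doses are 1000 mg against 600 × 1.8 = 1080 mg, whereas the full doses run the other way (1500 against 1000 mg/m²).

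**3. Where do Section 6.3.1 and Table 6-2 differ?**

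| Rule in Table 6-2 | Applies in Induction 2 by the table? | By the Section 6.3.1 sentence? |
|---|---|---|
| Stop for the rest of the cycle at grade 2 or higher neurotoxicity | Yes | Doubtful |
| Other reductions under institutional guidelines | Yes | No |
| Fixed reduced dose at re-challenge | No, next consolidation cycle only | No |

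The fixed reduced dose is therefore not in conflict. The difference is confined to the first two rows.

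**4. Upper limit of the scope problem.** Induction 2 has 2 doses a day × 3 days = 6 doses. If neurotoxicity appeared after dose k and the stop rule were ignored, 6 − k doses would still be given: 5 after dose 1, and 1 after dose 5. If Table 6-2 is followed, the number is zero.

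**The case against.** The strongest reply is that no competent site would be misled. The starting dose in the same sentence is per m², Section 6.1.1 bases cytarabine on BSA, and the flat reading gives an absurd age ordering. The reduced dose is also an optional re-challenge. On scope, Section 6.3.1 sends the reader to Table 6-2 and forbids departures from mandatory modifications, and the table names Induction 2 twice. Neurologic checks accompany the Induction 2 infusions (Section 6.1.1.1), and Section 7.1.4 lets the investigator stop treatment judged harmful. Stopping may not even count as modifying a dose, because Section 6.3.1 separates interruptions from reductions. Chemotherapy rules are the same in both blinded arms. Finally, SAP Section 1 records that the trial stopped for futility on 23-Sep-2019, so a correction has little left to do in this trial.

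Most of this stands, and it sets the size of the point. Wrong action is unlikely, and the percentages and dose counts above are outer limits of a literal reading. But a reader who must infer the unit, or decide that the table overrules the text, is correcting the protocol rather than following it. The futility stop limits the practical benefit of a correction. It does not make the text right, and uncorrected wording can be carried into a later protocol.

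**Conclusion.** Both errors are present in the current protocol text, and both are minor. The first is a unit slip: 1 of 12 stated doses lacks /m², and 1000 mg/m² is the evident intent. Its worst case is a re-challenge dose 33% to 55% too low, which requires a literal flat-dose reading and rests on the assumed BSA range of 1.5 to 2.2 m². The second is a summary sentence narrower than the table it introduces. It leaves doubt over the stop rule and institutional reductions in Induction 2, but has no effect where the table is followed. Neither touches sample size, power, type I error, any endpoint or the comparison between arms.

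**What to change.** In Table 6-2, give the reduced cytarabine dose for patients under 60 as 1000 mg/m². In the cytarabine paragraph of Section 6.3.1, name Induction 2 alongside consolidation so that the sentence has the same scope as the table. The cost is two wording corrections in a protocol clarification or the next amendment, with no change to design, sample size or analysis.
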